Cardiac magnetic resonance (CMR) imaging is increasingly being used in the assessment of regional and global left ventricular function at rest and during vasodilator stress (16-18). CMR has many important technical advantages including a higher spatial resolution than PET or SPECT, improved tissue characterization (both with and without contrast), and superior repeatability and endocardial definition (including functional assessment) over echocardiography. Its power of tissue characterization is particularly highlighted with the use of late gadolinium enhancement (LGE) and its excellent spatial correlation with infarction, necrosis, and fibrosis (19). With respect to wall motion, myocardial strain imaging with CMR uses magnetic saturation "tag" lines (figure 1) to aid in qualifying and quantifying wall motion, is superior to echo-based strain techniques, and has been demonstrated to correlate well with LVEF (20-23).

At this time, there is ample evidence that vasodilator stress induces functional changes (4-7,9,11,12); however, without an understanding of the etiology of this process, its value in patient management is limited. In order to use functional changes induced by vasodilator stress, it is necessary to first understand the relationship between functional and perfusion abnormalities, local strain and fibrotic burden.

It is the intent of this research to quantify the effects of regadenoson on myocardial function and contraction in the presence of CAD. We are proposing a CMR protocol to evaluate myocardial viability and function, with CMR tagging, on a segment-based approach. We plan to evaluate correlations in wall motion changes (ie. - myocardial radial strain (ΔR) and/or displacement ($\Delta\theta$)) during regadenoson stress and correlate with areas of myocardial infarction (late gadolinium enhancement on CMR), areas with identified perfusion defect (on PET), and a change in LVEF magnitude (on both PET and CMR).

Figure 1: Tagged short axis cine view of the left ventricle (left panel) and late gadolinium enhancement image (right panel) showing a near transmural infarction of the septal wall.

HYPOTHESIS

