The hypothesis of this study is that in a population with a demonstrated perfusion defect and WMA (measured by Rb-82 PET), regadenoson stimulates changes in ventricular mechanics (radial strain and rotational displacement) and LVEF associated with the degree of ischemic or fibrotic burden. Additionally, these changes may be different for normal, ischemic, and infarcted myocardium and will be compared between a high-risk population and a cohort of low-likelihood normals.

PRIMARY END-POINTS

For each patient group, every segment of the myocardium will be classified as normal, reversible, or non-reversible based on the PET perfusion data. Then for each segment category the radial strain (ΔR) and rotational displacement ($\Delta\theta$) will be calculated using an industry

standard CMR software package (current plans are to use HARP®, Diagnosoft, Morrisville, NC, though another package may be used). These values will be determined from tagged cine images obtained in three short axis (apical, mid, and basal) views of the left ventricle obtained during regadenoson induced stress and at rest (or difference in stress values).

1. Primary End-Point 1 of this study is to determine if there is a measurable difference in the strain (ΔR) and/or displacement ($\Delta\theta$) of normal and abnormal segments between the defined ischemic and normal patient groups.
2. Primary End-Point 2 of this study is to determine if there are measurable differences in the strain (ΔR) and/or displacement ($\Delta\theta$) between segment classifications (normal, reversible, and non-reversible perfusion defects).

SECONDARY END-POINTS

Secondary end-points will be determined from tagged cine images obtained in three short axes (apical, mid, and basal) views of the left ventricle obtained during regadenoson induced stress and at rest (or difference in stress values).

1. Secondary End-Point 1 of this study is to determine the strain (ΔR) and/or displacement ($\Delta\theta$) scores correlate with flow reserve as measured by PET and/or transmural extent of infarction (TEI) indicated by Late Gadolinium Enhancement (LGE).
2. Secondary End-Point 2 of this study is to track any adverse events as a result of participation in this study.

STUDY DESIGN

Subjects who have had a clinically indicated, ECG-gated, Rb-82 myocardial perfusion PET study will be recruited for participation. Specific inclusion/exclusion criteria are:

Inclusion Criteria

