Consented subjects will be asked to undergo a rest/Lexiscan® (Regadenoson) stress cardiac MRI examination. For patients who do not have an estimated glomerular filtration rate on record within 6 months of participation, a creatinine will be drawn as part of the screening procedures. Patients with renal dysfunction (defined as an estimated glomerular filtration rate (GFR) < 60 mL/min/1.73m² within 6 months of participation) or a history of gadolinium contrast allergy or intolerance will participate in an abridged non-contrast protocol consisting of the localizer, functional and stress imaging sequences only, and no contrast will be administered.

There will be 40 subjects recruited into this study. 15 subjects will be recruited who had normal perfusion, normal LVEF and no WMA on a clinically indicated cardiac PET study. 25 subjects will be recruited into the ischemic cohort. Consented study participants will receive one dose of Lexiscan® (Regadenoson) while taking part in this protocol.

Ischemic Patient Population

The abnormal population will be selected from a group of patients with a clinically indicated myocardial perfusion PET study demonstrating reversible ischemic perfusion defect, a rest LVEF of $\geq 35\%$, and demonstrated WMA by quantitation, utilizing QPET's QGS analysis program

(Cedars Sinai Health System, Los Angeles, CA). A WMA will be defined as having a drop in LVEF from rest to stress and/or an extent of greater than or equal to 10% thickening and/or motion.

Myocardial perfusion rest/Regadenoson PET protocol

All PET studies will have been clinically indicated and performed prior to study participation. These studies will have been performed on a Biograph™-16 or Biograph™-64 PET/CT or Siemens ACCEL Dedicated PET system (Siemens Medical Solutions, Erlangen, Germany).

Biograph™-16 or Biograph™-64 PET/CT System

A low-dose CT image acquisition will have been acquired for attenuation correction. The resting perfusion images will have been acquired using 20-40 mCi of Rubidium-82, infused over 35 seconds. The ECG gated, list mode acquisition will have started prior to the start of the rubidium-82 infusion and continued for 7 minutes.

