The patient to patient variability of normal resting LVEF is 5.3% (3). For the normal patients, there is an expected increase in ejection fraction of 8% (3). For ischemic patients, we have defined a change in ejection fraction of 2% as being significant. The net change would be a 10% change in difference in ejection fraction between the control (normal) and the ischemic groups.

If we assume cylindrical geometry, this would imply a roughly 5.6% change in the radius of the myocardium would result in a change in ejection fraction of 10% (assuming a resting LVEF of 55). Based on (3), this would give a Cohen's d of 1.06 and a total of 16 patients per group. However, given the need to explore the abnormal arm of the study, can obtain a similar power of 0.8 using an unequal population sizes of 13 (normal) and 22 (abnormal). We anticipate approximately 15% of patients that may not achieve sufficient quality of data would yield population of 15 normal subjects and 25 ischemic subjects to achieve the 0.8 power.

RESEARCH ENVIRONMENT

ASPIRE Foundation

Study funding will be provided by Astellas to the sponsor, the ASPIRE Foundation. The ASPIRE Foundation is a not-for-profit, non-invasive, imaging-based foundation dedicated to furthering knowledge about the role of imaging in improving patient outcomes. The ASPIRE Foundation is a joint venture between Saint Luke's Cardiovascular Consultants, the Mid America Heart Institute, and Cardiovascular Imaging Technologies. The ASPIRE Foundation will subcontract with Cardiovascular Imaging Technologies for staff to conduct its trials. Only CVIT study-

specific staff (Co-PIs: Drs. [name] and [name]; Sub-PIs: Drs. [name] and [name]; and Study Coordinators: [name] and [name]) will have access to patient data.

Saint-Luke's Cardiovascular Consultants

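### The power of 0.8 rests on a d of 1.06 that appears to divide a change in radius by the SD of resting LVEF, and it is not shown for radial strain or rotational displacement

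*Combined protocol and SAP*

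**What the plan says.** The Powering Calculation proceeds in four steps.

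- It gives one measure of spread: "The patient to patient variability of normal resting LVEF is 5.3% (3").
- It expects LVEF to rise by 8% in normal patients and treats a 2% change in ischemic patients as significant. It then combines the two: "The net change would be a 10% change in difference in ejection fraction between the control (normal) and the ischemic groups".
- It moves to the radius by assuming a cylinder and a resting LVEF of 55: "this would imply a roughly 5.6% change in the radius of the myocardium would result in a change in ejection fraction of 10"%.
- It concludes: "Based on (3), this would give a Cohen's d of 1.06 and a total of 16 patients per group". It then says that 13 normal and 22 abnormal patients give similar power of 0.8, and recruits 15 and 25 to allow for about 15% with inadequate data.

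The primary endpoints are different variables. Under Primary End-Points and Primary End-Point Analysis they are radial strain and rotational displacement from tagged CMR, by segment class. Primary End-Point 1 compares these measures "of normal and abnormal segments between the defined ischemic and normal patient groups"; Primary End-Point 2 compares segment classes. The only link between strain and LVEF is a background remark, before the Hypothesis, that tagged strain "has been demonstrated to correlate well with LVEF".

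**The concern.** A Cohen's d needs its difference and its SD on the same variable and scale. Here the step just before d yields a percent change in radius, while the only SD available is for LVEF. That SD is also cross-sectional, at rest and in normals, whereas the effect is a between-group difference in rest-to-stress change. By its title the cited source is a PET study, while the endpoints are measured by CMR tagging.

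The 10% is not defined as LVEF points or as a relative change, and neither alpha nor sidedness is stated.

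This paragraph is the only justification for the sample size. If strain or rotation shows no difference, the result will be read against a power of 0.8 that was never derived for either measure.

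**Working it through.** **Inputs** (Powering Calculation): effects 2, 8, 10 and 5.6%; SD 5.3%; resting LVEF 55; evaluable patients 13 + 22. Assumed, because not stated: two-sided alpha 0.05. Power is from the noncentral t for a two-sample t-test.

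**1. Reproducing d and N.** Each printed effect over the one printed SD:

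| Effect | Divided by 5.3 |
|---|---|
| 2 | 0.38 |
| 8 | 1.51 |
| 10 | 1.89 |
| 5.6 | 1.057 |

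Only 5.6/5.3 rounds to 1.06. The nearest other construction tried, 8/(5.3√2) = 1.067, rounds to 1.07. At d = 1.0566, power is 0.798 with 15 per group and 0.824 with 16, so 16 is the answer. That agrees with the plan but is not specific, since any d from 1.024 to 1.0598 gives 16. Power at 13 + 22 is 0.83 to 0.84. The step from d to N is therefore sound; the question is how d was formed.

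**2. What 10% means.** On a cylinder, LVEF = 1 − (ESR/EDR)², with ESR and EDR the end-systolic and end-diastolic radii. At LVEF 55, ESR/EDR = √0.45 = 0.6708.

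- Relative 10% fall (to 49.5): ESR/EDR = √0.505 = 0.7106. The change is 5.93% of the baseline ESR or 5.60% of the post-change ESR.
- Relative 10% rise (to 60.5): 6.31% of baseline or 6.74% of post-change ESR.
- 10 points (to 45 or 65): 10.55% or 11.81% of baseline ESR; 9.55% or 13.39% of post-change ESR.

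The printed 5.6% thus fits a relative change, and exactly only a fall expressed on the post-change radius. Yet 8 + 2 = 10 reads more naturally as points.

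**3. Effect and SD on one scale and one base.** The resting SD is used here as the SD of change. To first order, an SD of 5.3 points is 5.3/(2 × 0.45) = 5.89% of baseline ESR. On the post-change radius after the relative fall it is 5.89 × 0.6708/0.7106 = 5.56%.

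| Reading | d | Power at 13 + 22 |
|---|---|---|
| 10% relative, LVEF: 5.5/5.3 | 1.04 | 0.82 |
| 10% relative fall, baseline radius: 5.93/5.89 | 1.01 | 0.80 |
| 10% relative fall, post-change radius: 5.60/5.56 | 1.01 | 0.80 |
| 10% relative rise, baseline radius: 6.31/5.89 | 1.07 | 0.84 |
| 10 points, LVEF: 10/5.3 | 1.89 | >0.99 |
| 10 points, baseline radius: 10.55/5.89 to 11.81/5.89 | 1.79 to 2.01 | >0.99 |

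**4. Resting SD against SD of change.** With equal variances at rest and stress, SD of change = 5.3√(2(1 − ρ)), which equals 5.3 only at ρ = 0.5. For assumed ρ of 0.25, 0.5 and 0.75 the SD is 6.49, 5.30 and 3.75. Power for 5.5 LVEF points is then 0.65, 0.82 and 0.98; for 10 points it is about 0.99 or more throughout.

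**5. The primary endpoints.** Steps 3 and 4 concern LVEF or radius. For strain there is no SD; for rotation there is neither SD nor target. No power follows from the documents. As illustration only, treating 5.6 as a strain difference in strain units, an assumed SD of 4, 6, 8 or 10 gives power 0.97, 0.74, 0.49 or 0.34 at 13 + 22.

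**6. What the sample size alone supports.** The standardised difference with 80% power is 1.01 at 13 + 22. At 12 + 21 it is 1.05 (15 × 0.85 = 12.75 and 25 × 0.85 = 21.25, rounded down).

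**The case against.** Three points can be made for the plan.

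First, d is attributed to a cited source, which may hold another SD. An SD near 9.4 would give 1.06 for a 10-point difference (10/1.06 = 9.43). This stands as a limit: 5.6/5.3 is a reconstruction from the printed figures, not a documented step. It does not supply a strain or rotation SD.

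Second, mixing scales hardly changes N. If 10% is relative, LVEF over LVEF gives 5.5/5.3 = 1.04 and again 16 per group; if it is points, the plan is conservative. This also stands. A reader might divide the printed 5.6% by the 5.89% SD and infer that consistent scaling drops power clearly below 0.8. That comparison mixes bases, because 5.6% is exact only on the post-change radius and 5.89% is on the baseline radius. On a common base power is about 0.80.

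Third, the radius may be meant as a proxy for radial strain. It can serve at most as a crude target. A good correlation with LVEF does not carry over an SD, and nothing in the paragraph bears on rotation.

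The strain SDs of 4 to 10 and the correlations of 0.25 to 0.75 have no source in the documents. They show sensitivity and should not be used as thresholds.

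**Conclusion.** The concern holds as a gap in justification. The stated 0.8 is not shown for radial strain or rotational displacement, the two primary measures. The printed d most likely puts a change in radius over a cross-sectional SD of resting LVEF, with the 10% undefined and alpha and sidedness missing.

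The mismatch of scale by itself is numerically small. With the resting SD as the SD of change and two-sided 0.05, consistent readings give about 0.80 to 0.84 for a relative 10% LVEF change and above 0.99 for 10 points. The choice of SD matters more under the relative reading: at an assumed rest-stress correlation of 0.25, power for 5.5 LVEF points is 0.65.

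A reader might infer that the trial is underpowered. The documents do not support that: without a strain or rotation SD, true power could be higher or lower than 0.8. This should be fixed, but it gives no reason to change the sample size.

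**What to change.** Keep 15 + 25 and revise the Powering Calculation as follows.

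1. Withdraw d = 1.06 and power 0.8 as the power for strain and rotation. If the present calculation stays, label it LVEF-based, say whether 10% is points or relative, use an SD of the rest-to-stress change on the same scale, and state alpha and sidedness.
2. For the primary endpoints, do one of two things:
   - Give a sourced SD and target difference for the chosen strain measure and recompute. The reference list already has a stress/rest tagged-strain study, though its title says circumferential rather than radial strain.
   - Or state that 13 + 22 evaluable patients give 80% power for a standardised difference of 1.01 (1.05 at 12 + 21) in a two-sided 0.05 two-sample t-test on one per-patient summary.
3. The sponsor should name that summary and contrast, because Primary End-Point Analysis leaves open rest and stress values or their difference. One example is the per-patient mean stress-minus-rest change in radial strain. In choosing the contrast, note that the controls are selected for normal perfusion ("15 subjects will be recruited who had normal perfusion, normal LVEF and no WMA on a clinically indicated cardiac PET study") and the ischemic group for a PET study "demonstrating reversible ischemic perfusion defect". Abnormal segments should therefore come from the ischemic group only.
4. State that no power is claimed for rotational displacement or Primary End-Point 2 unless inputs are supplied.

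The cost is textual: no more patients and no change in procedures. The power claim becomes less favourable. A detectable standardised difference follows from the sample size alone and does not show that an effect of that size is plausible.
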